6 STUDY OBJECTIVES

The primary objective of this study is to estimate the ORR for the combination of CDX-3379 in combination with cetuximab in patients with cetuximab-resistant advanced HNSCC

The secondary objectives of this study are to:

- Estimate the clinical benefit response (CBR), duration of response (DOR), progression-free survival (PFS), and overall survival (OS) for patients with cetuximab-resistant advanced HNSCC treated with CDX-3379 in combination with cetuximab
- Evaluate the safety of CDX-3379 in combination with cetuximab
- Evaluate the PK of CDX-3379 in combination with cetuximab
- Evaluate the anti-drug antibodies (ADA)/immunogenicity of CDX-3379 in combination with cetuximab
- Evaluate tumor DNA biomarkers for CDX-3379 in combination with cetuximab and assess correlation with efficacy.

█ [REDACTED]

█ [REDACTED]

7 INVESTIGATIONAL PLAN

7.1 Overall Design and Plan of the Study

This is an open-label, multicenter Phase 2 study of CDX-3379 in combination with cetuximab in patients with cetuximab-resistant HNSCC. Patients will be treated with CDX-3379 plus cetuximab until progressive disease, unacceptable toxicity, or other criteria for discontinuation of study treatment (Section 7.4.1) are met.

The study was initially designed according to a Simon's 2-stage design in which one tumor response (CR or PR) would need to be observed in the first 13 evaluable patients before completion of accrual to a total of 27 evaluable patients. Patients who discontinue treatment in the absence of progression/symptomatic deterioration/death before the first tumor assessment will be considered unevaluable for primary analysis and will be replaced. Following completion of stage 1 of the study, where 1 complete response was observed, emerging biomarker data were reviewed to assess correlation with efficacy. In the overall CDX-3379 development program, in a small patient dataset, FAT1 and NOTCH1, NOTCH2 and NOTCH3 mutations appeared to be associated with clinical activity including objective response and durable stable disease. Given these findings, the study design has been amended to enroll up to approximately 45 total patients, including at least 15 patients whose tumor harbor a FAT1 mutation based on retrospective gene sequencing. Screening tissue samples will be required to be submitted as directed by the Sponsor at the time of enrollment to allow for gene sequencing and tracking the number of patients whose tumor harbor a FAT1 mutation.

Tumor assessments will be performed approximately every 6 weeks during treatment. Patients who discontinue treatment in the absence of progression will continue to have assessments approximately every 12 weeks until documented progression or initiation of alternate anticancer therapies. Tumor response will be assessed by the investigator in accordance with RECIST 1.1 guidelines (Eisenhauer, et al. 2009) (Section 10.2.1 and Appendix 2).

Continuous evaluation of toxicity will be performed by the investigators and Celldex throughout the entire course of patient treatment and through 30 days following the last dose of CDX-3379. Subsequently, patients will be followed for survival, with contact every 12 weeks until study closure.

7.2 Selection of Study Population

7.2.1 Number of Patients

It is anticipated that approximately 45 patients will be accrued. Enrollment will be competitive with no maximum per site.

7.2.2 Patient Eligibility

7.2.2.1 Inclusion Criteria

Patients may be included in the study only if they meet all of the following inclusion criteria prior to receiving study treatment:

1. Read, understood, and provided written informed consent, and if applicable, Health Insurance Portability and Accountability Act (HIPAA) authorization, after the nature of the study has been fully explained, and must be willing to comply with all study requirements and procedures.
2. Male or female patients who are 18 years of age or older.
3. Histologically or cytologically confirmed HNSCC that is recurrent or metastatic, not curable with local treatment modalities (e.g., surgery, radiation), and progressive (based on radiographic, clinical or pathologic assessment) during or subsequent to last therapy.
4. Human papilloma virus (HPV) negative tumor, as established by the local site. Acceptable standards include p16 immunohistochemistry (where a tumor is classified as p16-positive when showing diffuse nuclear and cytoplasmic staining in at least 70% of tumor cells) and/or assessment of HPV deoxyribonucleic acid (DNA).
5. Prior treatment must include (in any combination or sequence):
 - a. check-point inhibitor targeting programmed death receptor-1 axis (PD-1/PDL-1), unless not a candidate
 - b. cetuximab, with tumor progression during or within 6 months after completing treatment (regardless of any intervening therapies)
6. Measurable (target) disease by RECIST 1.1 criteria ([Eisenhauer, et al. 2009](#)) ([Appendix 2](#)). Target lesions selected for tumor measurements should be those where additional (e.g., palliative) treatments are not indicated or anticipated.
7. Willingness to consent for tumor biopsy from an accessible site (primary or metastatic) prior to initiating study therapy. In cases where a fresh biopsy is not feasible (i.e., if an accessible site cannot be biopsied with acceptable clinical risk or upon patient refusal), archival tissue may be submitted instead, after discussion with and approval by the medical monitor.
8. All residual toxicity related to prior radiotherapy or anticancer therapies (excluding alopecia, grade 2 fatigue, vitiligo or endocrinopathies on stable replacement therapy) must resolve to grade 1 severity or less (or returned to baseline) prior to receipt of study treatment.
9. Adequate electrolytes, liver, renal, and hematology function as defined below:
 - a. Hemoglobin \geq 9 g/dL
 - b. Absolute neutrophil count \geq 1500/mm³
 - c. Platelet count \geq 100,000/mm³
 - d. Aspartate aminotransferase (AST) and alanine aminotransferase (ALT) \leq 2.5 \times upper limit of normal (ULN) (\leq 5 \times ULN for cases involving liver metastasis)
 - e. Bilirubin \leq 1.5 \times ULN (\leq 5 \times ULN for cases of documented or suspected Gilbert's disease)

- f. Serum creatinine \leq 1.5 g/dL or calculated creatinine clearance (CrCl) \geq 60 mL/min for patients with serum creatinine $>$ 1.5 x ULN
- g. Serum magnesium \leq 1.5 \times ULN
- h. Serum calcium and potassium within normal limits

10. Life expectancy \geq 12 weeks

11. Eastern Cooperative Oncology Group (ECOG) Performance Status of 0 or 1 ([Appendix 3](#))

12. Both male and female patients enrolled in this trial must agree to use highly effective contraception during the course of the trial and for at least for 6 months after the final dose of CDX-3379 or cetuximab, whichever is later. Patients and/or partners who are surgically sterile or postmenopausal are exempt from this requirement.

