11. A marked baseline prolongation of QT/QTc interval (e.g., repeated demonstration of a QTc interval > 450 ms); additional risk factors for torsades de pointes (TdP) (e.g., a history of heart failure, family history of Long QT Syndrome, or active hypokalemia,); the use of concomitant medications that prolong the QT/QTc interval; significant cardiovascular disease including unstable angina pectoris, uncontrolled hypertension or arrhythmia, congestive heart failure (New York Heart Association Class III or IV) related to primary cardiac disease, uncontrolled ischemic or severe valvular heart disease; or any of the following within 6 months prior to the first dose of study treatment: myocardial infarction, severe/unstable angina, coronary artery bypass graft, congestive heart failure, cerebrovascular accident, transient ischemic attack.
12. Requirement for chronic immunosuppressive medication including systemic corticosteroids above the physiologic dose (defined as 30 mg/day hydrocortisone or the equivalent).
13. Any other acute or chronic medical or psychiatric condition or laboratory abnormality that could increase the risk associated with trial participation or trial drug administration or could interfere with the interpretation of trial results and, in the judgment of the investigator, would make the patient inappropriate for entry into the trial.
14. Known alcohol or drug abuse.
15. Women who are pregnant or nursing. All female patients with reproductive potential must have a negative pregnancy test prior to starting treatment
16. Known allergy or past administration reaction including infusion reactions, anaphylactic, or anaphylactoid reactions to any component of the CDX-3379 formulation.
17. Prior history of clinically significant hypersensitivity reaction or significant intolerance to cetuximab; history of allergic reactions attributed to compounds of chemical or biologic composition similar to those of cetuximab.

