10.1.1 Screening Phase

Prior to the performance of any study-specific procedures, the patient will have the nature of the study explained to him/her, and will be asked to give written informed consent and if applicable, HIPAA authorization. Informed consent/HIPAA authorization must be obtained prior to any study-specific procedures that do not form a part of the patient's normal care. However, assessments performed according to standard of care prior to receipt of informed consent may be utilized to fulfill the screening requirement, if completed within the required window for screening.

The assessments outlined in for the Screening Visit in the Schedule of Assessments ([Table 1](#)) will be completed for each patient prior to inclusion in the study. The screening evaluations may be carried out over more than one visit.

Patients who are screened but do not meet all entry criteria (i.e., screen failures) will not be entered in the clinical database. Instead, a log of patients screened for the study, including the reason for study ineligibility, will be maintained at the study center. Once assigned, patient numbers for any screening failures, non-treated, unevaluable, or discontinued patients will not be re-used.

Study enrollment will occur only after confirming all inclusion criteria and none of the exclusion criteria have been met, and in accordance with instructions provided by Celldex.

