10.2.5.5 Laboratory Safety Data

The following clinical laboratory tests will be performed at the study visits outlined in [Table 1](#).

Table 10: Clinical Laboratory Tests to be Performed During Study

Hematology:	Clinical Chemistry:	Urinalysis
Hemoglobin*	Sodium*	Protein
Hematocrit*	Potassium*	Glucose
Mean corpuscular volume (MCV)	Chloride*	Specific gravity
Erythrocyte count (RBC)	Bicarbonate*	Blood
Leukocytes (WBC)*	Glucose (nonfasting)	
Platelets*	Blood urea nitrogen (BUN)*	
Differential:*	Creatinine*	Microscopic examination will be performed if indicated
Neutrophils	Calcium*	
Lymphocytes	Magnesium*	
Monocytes	Phosphate	
Eosinophils	Alkaline phosphatase*	
Basophils	Alanine transaminase (ALT/SGPT)*	
	Aspartate transaminase (AST/SGOT)*	
Differential should be reported consistently throughout the study as either an absolute count (preferred) or as a percentage.	Total protein	
	Albumin	
	Lactate Dehydrogenase (LDH)	
	Total Bilirubin*	
	Uric acid	
	Amylase*	
	Lipase*	
Coagulation Panel		
Prothrombin time (PT)/		
Partial thromboplastin time (PTT)		
International normalized ratio (INR)		
The coagulation panel should be done at screening		

* On study treatment days, tests must be performed within 24 hours prior to dosing, and results must be reviewed prior to study treatment administration. For all other laboratory tests, results from the prior visit must be reviewed before the administration of study treatment. See Section 8.2 for guidance regarding dosing modifications/delays due to toxicity, including laboratory abnormalities.

Investigators must document their review of each laboratory report by signing or initialing and dating each report, as well as addressing the clinical significance and causality (for significant abnormalities). Clinically significant abnormal laboratory results should be repeated as soon as possible (preferably within 24 to 48 hours). Section 10.2.5.1 provides further guidance as to when abnormal laboratory results are to be reported as adverse events.

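### Inclusion criterion 9f caps serum creatinine at 1.5 g/dL (1,500 mg/dL), so the renal criterion excludes nobody, and changing only the unit may leave cap and CrCl trigger mismatched.

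*Protocol*

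**What the plan says.** Protocol 7.2.2.1 admits patients "only if they meet all of the following inclusion criteria", so each item in the list must be satisfied separately. Criterion 9f is the renal item and has two clauses:

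- **Creatinine clause.** Serum creatinine must be at or below the printed limit. The limit and the connector to the next clause read "1.5 g/dL or calculated creatinine clearance (CrCl".
- **Clearance clause.** CrCl must be at least "60 mL/min for patients with serum creatinine" above 1.5 × ULN.

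The neighbouring items work in multiples of ULN. Criterion 9d (transaminases) gives a wider multiple of "ULN for cases involving liver metastasis", 9e (bilirubin) does the same with a multiple of "ULN for cases of documented or suspected" Gilbert's disease, and 9g sets magnesium at 1.5 × ULN. The unit g/dL also appears in 9a, where it is correct for hemoglobin.

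SAP 2.5 (Exhibit 5) gives no renal number and sends the reader back to the protocol. Laboratory tests are done locally (Protocol Table 1, footnote 11), and neither document gives a creatinine ULN.

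**The concern.** Among the eligibility criteria that can be read, 9f is the only numeric renal threshold. If its cap lies far above any creatinine value a patient could have, the criterion does nothing. The clauses are alternatives, so passing the first makes the clearance test irrelevant. A patient with poor renal function would meet 9f, and no eligibility deviation against it (SAP 5.3) could ever be recorded.

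The obvious repair, g to mg, has a problem of its own. The cap would be an absolute concentration, but the clearance route would still open only above a multiple of the local ULN. Those two points coincide at one ULN value only. Elsewhere the rule either leaves a band of patients with no route to eligibility or lets the clauses overlap.

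**Working it through.** **Inputs from the protocol:** cap 1.5 g/dL; clearance limit 60 mL/min; clearance trigger 1.5 × ULN; clauses joined as alternatives (all from 9f).

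**Assumptions, not in the documents:** serum creatinine up to about 30 mg/dL; local ULN between 0.9 and 1.4 mg/dL.

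**Step 1: the cap as printed.** 1.5 g/dL × 1,000 mg/g = 1,500 mg/dL, and 1,500 / 30 = 50, so the cap is 50 times the assumed extreme. The rule, with SCr in mg/dL, is:

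SCr ≤ 1,500, or (SCr > 1.5 × ULN and CrCl ≥ 60).

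It was run on a grid of 300 creatinine values (0.5 to 30.4 mg/dL) by 6 ULN values, 1,800 points in all. Every point passed, and changing CrCl from 120 to 10 mL/min altered the result at none.

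**Step 2: only the unit corrected.** The rule becomes SCr ≤ 1.5, or (SCr > 1.5 × ULN and CrCl ≥ 60). Compare the trigger with the cap:

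| Assumed ULN (mg/dL) | 1.5 × ULN | Minus 1.5 | Result |
|---|---|---|---|
| 0.9 | 1.35 | −0.15 | clauses overlap from 1.35 to 1.5 |
| 1.0 | 1.50 | 0 | clauses meet |
| 1.1 | 1.65 | +0.15 | no route above 1.5 and up to 1.65 |
| 1.2 | 1.80 | +0.30 | no route above 1.5 and up to 1.80 |
| 1.3 | 1.95 | +0.45 | no route above 1.5 and up to 1.95 |
| 1.4 | 2.10 | +0.60 | no route above 1.5 and up to 2.10 |

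**Step 3: two consistent repairs.**

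- Option A: SCr ≤ 1.5 × ULN, or CrCl ≥ 60.
- Option B: SCr ≤ 1.5 mg/dL, or CrCl ≥ 60.

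**Step 4: the same patients under each rule.**

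| SCr | CrCl | ULN | As printed | Unit only | A | B |
|---|---|---|---|---|---|---|
| 3.0 | 20 | 1.2 | in | out | out | out |
| 1.7 | 70 | 1.2 | in | out | in | in |
| 1.9 | 65 | 1.2 | in | in | in | in |
| 1.8 | 40 | 1.2 | in | out | in | out |
| 1.4 | 50 | 0.9 | in | in | out | in |

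The first row shows the printed rule admitting a patient whom every repair rejects. Rows two and three show the unit-only rule rejecting the better renal function and admitting the worse. The last two rows show that A and B differ in both directions.

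**Step 5: can such clearances occur in the gap?** The protocol names no CrCl formula. By Cockcroft-Gault, for an assumed 45-year-old man of 90 kg, CrCl = (140 − 45) × 90 / (72 × SCr). This gives 8,550 / 122.4 = 69.9 mL/min at SCr 1.7 and 8,550 / 136.8 = 62.5 mL/min at SCr 1.9. At ULN 1.2 the unit-only rule would turn this man away at 1.7 and accept him at 1.9.

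**The case against.** The best defence is that this is a drafting slip that any site would see through. The same line names 1.5 × ULN as the point where clearance matters, so a reader can tell both that the unit is wrong and roughly where the limit lies. A reader who gives the qualifier effect would require CrCl of at least 60 above 1.5 × ULN, and then clearance does decide. That is a sensible reading, but it is Option A and not the printed text, and other sites could reasonably settle on 1.5 mg/dL instead.

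A second objection is that the gap belongs to a hypothetical correction. This is right as far as it goes. The gap needs an intended cap of 1.5 mg/dL, a unit-only edit and a ULN above 1.0 mg/dL. If 1.5 × ULN was meant, there is no gap at any ULN. The gap bears on how to make the repair; the defect in the present text does not depend on it.

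Third, there are backstops:

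- Exclusion 13 (Protocol 7.2.2.2) covers a "laboratory abnormality that could increase the risk associated with trial participation or trial drug administration", in the investigator's judgment.
- Enrollment proceeds "in accordance with instructions provided by Celldex" (Protocol 10.1.1).
- Creatinine is among the starred tests in Table 10, and on treatment days those "tests must be performed within 24 hours prior to dosing, and results must be reviewed prior to study treatment administration".
- Inclusion 8 requires residual toxicity from earlier anticancer treatment to have resolved to grade 1 or less, or to baseline.

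These make harm less likely, but none of the text that can be read sets a renal entry limit. The sponsor's instructions are not provided, and Section 8 is redacted, so neither can be credited or faulted.

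Finally, an m lost in reading the PDF cannot be ruled out, although mg reads correctly elsewhere. If one was lost, the 1,500 mg/dL point falls away, but the mismatch between an absolute cap and a ULN trigger remains.

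**Conclusion.** The concern holds. Followed as written, 9f excludes nobody and its clearance test never operates. The conversion to 1,500 mg/dL is exact. That every patient falls below it rests on physiology outside the documents, but the margin is so wide that no plausible range changes the conclusion. Nothing in the readable text corrects it, including the readable part of the summary of changes (Protocol Appendix 4).

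That a unit-only correction may fall short is a conditional conclusion. Over the assumed ULN range it leaves no gap at 1.0 mg/dL, an ineligible band 0.15 to 0.60 mg/dL wide at ULN 1.1 to 1.4, and an overlap of 0.15 mg/dL at 0.9. The documents do not show whether 1.5 × ULN or 1.5 mg/dL was intended. The match with the trigger in 9f and the format of 9d, 9e and 9g fits the former; a simple unit slip fits the latter.

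This is an error in an eligibility threshold that bears on patient safety, and it should be corrected. It does not touch the objective response rate, the sample size or the power figures, and there is no evidence that any patient was wrongly enrolled.

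**What to change.** Rewrite 9f so that cap and trigger use the same basis:

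- **Option A:** creatinine no higher than 1.5 × ULN; above that, calculated CrCl of at least 60 mL/min.
- **Option B:** the same rule with 1.5 mg/dL as both cap and trigger.

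The sponsor's clinical team has to confirm which was meant, because the choice has consequences. Where ULN is above 1.0 mg/dL, A raises the limit for entry without a clearance check (to 1.80 mg/dL at ULN 1.2 and 2.10 at ULN 1.4). Where ULN is below 1.0, A is the stricter rule.

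The cost is that decision and one line in the next amendment or a clarification letter. No procedure is added and no analysis changes. If enrollment has already closed, the sponsor should state which rule sites applied when eligibility deviations are reviewed under SAP 5.3.

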7.2.2.2 Exclusion Criteria

Patients will be excluded from the study for any of the following reasons:

- 1. Nasal, paranasal sinus, or nasopharyngeal carcinoma, aside from WHO Type I and II (keratinizing, non-EBV positive) nasopharyngeal carcinoma which will be allowed.
- 2. Received CDX-3379 or other anti-ErbB3 targeted agents previously.
- 3. Any concurrent chemotherapy, radiotherapy, immunotherapy, biologic or hormonal therapy for cancer treatment. Concurrent use of hormones for non-cancer related conditions (e.g., insulin for diabetes and hormone replacement therapy) is acceptable.
- 4. Other prior malignancy active within 3 years, except for localized prostate cancer, cervical carcinoma in situ, non-melanomatous carcinoma of the skin, stage 1 differentiated thyroid cancer or ductal carcinoma in situ of the breast that has/have undergone curative surgery or radiation.
- 5. Known brain metastases, unless previously treated and asymptomatic for 2 months and not progressive in size or number for 2 months prior to enrollment. Continued use of anticonvulsants (in the absence of any suspicion of progressive brain metastases) is acceptable.
- 6. Known HIV, hepatitis B or hepatitis C infection, or active infection requiring systemic intravenous therapy
- 7. Use of any monoclonal based therapies within 4 weeks (excluding cetuximab which does not require a wash-out), and all other immunotherapy (tumor vaccine, cytokine, or growth factor given to control the cancer) within 2 weeks, prior to the first dose of study treatment.
- 8. Chemotherapy within 21 days or at least 5 half-lives (whichever is shorter) prior to the planned start of study treatment
- 9. Major surgery within 4 weeks prior to the first dose of study treatment. Surgery requiring local/epidural anesthesia must be completed at least 72 hours before study drug administration and patients should be recovered.

10. Use of other investigational drugs within 2 weeks or 5 half-lives (whichever is longer) prior to study treatment administration
11. A marked baseline prolongation of QT/QTc interval (e.g., repeated demonstration of a QTc interval > 450 ms); additional risk factors for torsades de pointes (TdP) (e.g., a history of heart failure, family history of Long QT Syndrome, or active hypokalemia,); the use of concomitant medications that prolong the QT/QTc interval; significant cardiovascular disease including unstable angina pectoris, uncontrolled hypertension or arrhythmia, congestive heart failure (New York Heart Association Class III or IV) related to primary cardiac disease, uncontrolled ischemic or severe valvular heart disease; or any of the following within 6 months prior to the first dose of study treatment: myocardial infarction, severe/unstable angina, coronary artery bypass graft, congestive heart failure, cerebrovascular accident, transient ischemic attack.
12. Requirement for chronic immunosuppressive medication including systemic corticosteroids above the physiologic dose (defined as 30 mg/day hydrocortisone or the equivalent).
13. Any other acute or chronic medical or psychiatric condition or laboratory abnormality that could increase the risk associated with trial participation or trial drug administration or could interfere with the interpretation of trial results and, in the judgment of the investigator, would make the patient inappropriate for entry into the trial.
14. Known alcohol or drug abuse.
15. Women who are pregnant or nursing. All female patients with reproductive potential must have a negative pregnancy test prior to starting treatment
16. Known allergy or past administration reaction including infusion reactions, anaphylactic, or anaphylactoid reactions to any component of the CDX-3379 formulation.
17. Prior history of clinically significant hypersensitivity reaction or significant intolerance to cetuximab; history of allergic reactions attributed to compounds of chemical or biologic composition similar to those of cetuximab.

